#### 4.2 Exclusion Criteria.

Subjects will be excluded from enrollment if they meet any of the following criteria:

- Less than 1 incontinence accident (leak) per day\*
- Severe incontinence as determined by self-reported >5 accidents per day
- Currently pregnant, may be pregnant, attempting to become pregnant, or delivery within previous 6 weeks
- Vaginal or pelvic surgery within previous 6 months
- Severe Obesity as defined by BMI >= 35
- Change in incontinence medication type or dosing within the last 3 months.
- History or symptoms of urinary retention, extra-urethral incontinence, overflow incontinence
- Pelvic pain/painful bladder syndrome
- Active urinary tract infection (UTI) or history of recurrent UTIs (more than three in a year), or recurrent vaginitis (bacterial/fungal)
- Tissues protruding outside the vagina at rest
- Presence of incontinence-associated dermatitis or other perineal skin disorders or lesions,
- Complete denervation of the pelvic floor
- Conductive inter-uterine devise (IUD/Coil) or metal implants in the abdominal or pelvic area, including the hip and lumbar spine,
- Chronic coughing
- Previous use of Interstim device or Botox for UI
- Implanted cardiac device, untreated cardiac arrhythmia or suffer from other heart problems.
- Cancer, epilepsy or cognitive dysfunction
- Underlying neurologic/neuromuscular disorder
- Impaired decision making, suicidal thoughts, or drug/alcohol dependence
- Lacks capacity to consent for themselves.

## 4.3 Study Enrollment Procedures

The study uses the following multi-step process to achieve enrollment:

#### Recruitment

\* During the baseline week subjects will be excluded if they average less than 1 urge incontinence episode per day (with or without a leak).

- Ads placed in social media and other forums to attract candidates to a website that describes the study. These ads will be places in the US without regional geographic targeting and use key words including "incontinence" and "bladder leaks"
- Email to a list of women with urge incontinence who had previously expressed interest in participating in a clinical study.
- Alternately, healthcare providers who become familiar with the study can direct candidates
  to the study. These candidates will go through the same screening as all candidates and
  the referring healthcare provider would not be considered a study investigator. It is
  permissible for the referring healthcare provider to assist the candidates with completion
  of screening/consent information and to forward the information to Elidah.
- TR-1155-FORM-14 identifies the language that will be used in recruitment messaging.

# Screening

- Interested candidates complete an online survey comprising Screening Questions (TR-1155-FORM-13)
- Responses are maintained electronically in a Screening Log (TR-1155-FORM-11) which includes candidate contact information, date of survey completion, and survey responses.
- Survey responses will be reviewed to confirm that (based on IP addresses and/or provided contact info) candidates did not complete the survey multiple times with different responses, potentially in an attempt to qualify for enrollment.
- Hardcopy or verbal responses are acceptable and will be manually entered into the Screening Log.

#### Consent

- Candidates that meet the enrollment criteria based on responses to the screening survey are contacted by Elidah.
- Study personnel describe the study requirements, respond to any questions from the candidate and explain the consent process (see 11.2). Notes of this communication are maintained in the Case Report Form (TR-1155-FORM-10) if enrolled, or in the screening log if not enrolled.
- Consent documentation (TR-1155-FORM-5) is sent to the candidate either electronically or as a hardcopy.
- The candidate returns the signed consent form, or via an online option.
- The candidate is now considered a "subject", and a sequential Subject Number is assigned (TR-1155-FORM-7).
- A copy of the signed consent document is maintained in the subject's Case Report File.

#### Treatment Initiation

- Study materials are sent to the subject (see 10.1 and 10.2)
- Confirmation of eligibility is based on baseline data per 5.4.

## 4.4 Recruitment Strategies

Appreciating that achieving enrollment targets in a clinical study can be challenged by various factors, including difficulty in identifying qualified candidates, Elidah has implemented several strategies to mitigate such challenges including:

• Recruitment using social media allows access to thousands of women from across the US, which additionally encouraging participation from a diverse pool of candidates.

 Subjects will have access to the ELITONE-UUI device for \$100 deposit, which is a substantial discount compared to the commercially available ELITONE device which retails for \$399.

# 4.5 Retention Strategies

- Subjects who complete the study will receive their deposit back. If the subject does not complete all study requirements the Clinical Director has discretion to compensate with a lesser amount.
- Subjects will be informed that the device records usage/compliance.
- Bi-weekly monitoring of digital treatment diary by study staff, with email/phone follow-up as needed.

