## 5.4 Protocol Schedule

The study comprises five stages: Pre-study, Baseline, Verification, Treatment, and Post-Study.

- Pre-Study –The subjects initiate pre-study activity, which includes completion of the I-QoL Questionnaire and the Pre-study Incontinence History. The subject submits the pre-study materials to Elidah (electronically or hardcopy).
- **Baseline** –Concurrently, the subjects maintain the Daily Log for 7 days to establish a baseline of the episodes/day and pads/day measures. No treatment is administered during this period. After 7 days the subjects submit the data to Elidah (electronically or hardcopy). Subjects are instructed that they should not perform baseline activity during menses or if they are ill. Note that it is acceptable to complete or return the Pre-Study materials throughout this 7 day baseline period.
- **Verification** If the 7 day Baseline shows that the subject does not qualify based on urinary incontinence episode exclusion criteria (<1/day, >5/day) then the subject will be disqualified and the device will not be sent. The subject will be notified of disqualification, or if qualified, will be sent a link for deposit payment/hold. Qualifying subjects will be randomly assigned to a treatment group and a corresponding ELITONE-UUI device will be mailed to them.
- Treatment Subjects will self-administer treatment with the ELITONE-UUI device. Subjects will treat 5x/week for six weeks. Each treatment is 20 minutes. No more than one treatment per day. See Section 6 and Table 5-1 for a detailed description of the device and treatment regimen. If subjects are ill or in menses during the 6th study week they are instructed to extend treatment for at least 5 days after menses and/or they are in good health. During the treatment weeks subjects are required to maintain their Daily Log. There is no difference in treatment requirements between the two treatment groups.
- Post-Study Upon completion of treatment subjects complete the post-study requirements, which include the I-QoL questionnaire and a post-study usability questionnaire. Subjects are requested to complete the requirements and return the study materials to Elidah within 3 days of completing treatment. There is no difference in post-study requirements between the two treatment groups.

Table 5-1: Schedule of Subject Activities/Requirements.

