## 7.2 Risks and Side Effects

Participation in the study will expose the subjects to risks and side effects similar to users of electrical muscle stimulators (EMS) and transcutaneous electrical nerve stimulation (TENS) devices, both of which are low risk devices as evidenced by multiple products cleared for over-the-counter use. Note that many of the warnings and precautions associated with general use EMS and TENS devices (e.g. don't place electrodes over the eye) are less applicable to ELITONE-UUI due to the anatomic-specific nature of the ELITONE-UUI device. However, as with most medical devices, use of the product does carry health risks and potential medical side effects. Elidah does not foresee any psychological, financial, or legal risks to the subject associated with participation in the study.

The User Manual (TR-1155-FORM-12) identifies applicable warning and precautions. Each candidate receives a copy of these warnings and precautions as part of providing informed consent (see 11.2). Broadly categorized, these risks and side effects include:

- **Electrical Shock** The device delivers an electrical current to the body. Misuse of the device can result in an unintended shock which can be temporarily painful. Forms of misuse could include placing the electrode on another part of the body (e.g. across the chest) or turning the device on prior to applying the electrode to the body. The device, uses both hardware and software to control the output and has undergone extensive testing. As noted in 7.1, various safety measures are present to mitigate these risks.
- **Skin Irritation** Although the materials used in the electrode are biocompatible and used in similar, commercially available electrodes, there is a risk of skin irritation. This is likely to be

observed as persistent redness at the electrode application site, and is likely to resolve upon cessation of use.

Muscle Fatigue – The treatment is intended to exercise the pelvic floor muscles, and the
defined treatment regimen is guided by the recommended regimens of other EMS devices.
However, some subject may experience notable muscle fatigue, which, in the near-term, could
result in a temporary increase in urine leakage. Such occurrences are likely to resolve within
a matter of hours.

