#### 8. INTERVENTION DISCONTINUATION

Subjects in the study have the right to discontinue treatment at any point during the study and for any reason. If the subject chooses to discontinue, a reason for discontinuation will be recorded and every effort will be made for the subject to complete the post-study activities defined in Table 5-1.

Elidah may wish to discontinue intervention for a subject for a variety of reasons including those listed below. Effort will be made to bring the subject into study compliance prior to terminating participation.

- Purposeful improper use of the device
- Failure to treat per the assigned schedule
- A recurring adverse event or unanticipated problem.
- Failure to maintain the Daily Log for greater than 1 week

A pause on enrollment and/or treatment of active subjects may occur if Elidah discovers a serious issue with the device/treatment (see 7.3). Elidah maintains the right to discontinue the study at any point and for any reason. Stopping treatment does not pose any risk to subjects. The study may be discontinued at any time by the IRB, FDA, or other regulatory or government agency as part of their duties to ensure that research participants are protected.

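### The $100 deposit refund makes no exception for a woman who stops, or is withdrawn, because of an adverse event; this conflicts with Section 7.2 and gives her a financial reason to keep treating

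*Combined protocol and SAP*

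**What the plan says.** Section 4.4 gives the sum, in dollars, as "100 deposit, which is a substantial discount compared to the commercially available ELITONE device"; that device retails at $399. Section 5.4 places the payment after the seven-day baseline and before the device is mailed: the woman, "if qualified, will be sent a link for deposit payment/hold".

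Section 4.5, under retention, has two refund rules. For completers: "Subjects who complete the study will receive their deposit back". For all others: "If the subject does not complete all study requirements the Clinical Director has discretion to compensate with a lesser amount".

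Two other sections bear on this. Section 7.2 states: "Elidah does not foresee any psychological, financial, or legal risks to the subject associated with participation in the study". Section 8 states: "Subjects in the study have the right to discontinue treatment at any point during the study and for any reason". Among the reasons for which the sponsor may discontinue a woman, Section 8 lists: "A recurring adverse event or unanticipated problem".

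**The concern.** Safety is half of the primary endpoint (Section 2.2) and rests on adverse events in women who treat themselves at home. Much of that information comes from what the woman says or writes. A refund that depends on completion is meant to keep women in the study. With no exception for harm, it acts in the same way on a woman with skin irritation or muscle fatigue, both of which Section 7.2 names as foreseeable.

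Two things are at stake. One is fairness: she may bear a money loss that follows from a device effect, although the protocol says it foresees no financial risk. The other is the safety data: an incentive to continue prolongs exposure in the women who have symptoms and, if it also discouraged reporting, would tilt the safety result towards a favourable picture.

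**Working it through.** The plan gives no figure to reproduce, so the main check sets the sections side by side.

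1. **Is a woman who stops for an adverse event caught by the rule?** Yes, as written. Section 4.5 knows only completers and women who have not met every requirement. Section 5.5 counts at least 20 of the 30 sessions, plus the pre-study, baseline and post-study tasks, as adherence. Whether completion in 4.5 means the same is not stated. A woman who stops early and falls short is in the second class, and 4.5 gives that class no route to a full refund.

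2. **Is a woman withdrawn by the sponsor caught?** Yes. Withdrawal for a recurring adverse event under Section 8 also leaves requirements unmet, and neither section mentions the deposit in that case.

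3. **Does this fit Section 7.2?** No. That section expects skin irritation to resolve once use ends, so stopping is a foreseeable response to it, and stopping puts up to $100 at risk. Section 7.4 has the sponsor cover medical costs of device injury if the protocol was followed, but it is silent on the deposit.

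4. **Does it fit Section 8?** There is tension, not contradiction. The right to stop remains, but Section 8 does not describe it as free of cost.

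5. **How does it reach reporting?** Only indirectly: repeated reports may lead to sponsor withdrawal, and withdrawal to a smaller refund. A woman who reports an event and completes loses nothing.

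**Scale of the money.** Inputs: 40 completers wanted and 50 to 55 enrolled (Section 5.2); $100 each (Section 4.4).

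- Non-completers: 50 − 40 = 10, to 55 − 40 = 15.
- Share: 10/50 = 20%, to 15/55 = 27%.
- Largest total deposits affected: 10 × $100 = $1,000, to 15 × $100 = $1,500.

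This is an upper bound. A woman becomes a subject at consent (Section 4.3), while the deposit is requested only after baseline verification (Section 5.4), so some of the 10 to 15 may never have paid. The number stopping for adverse events is not given.

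**Illustration of direction only.** Assume a true per-woman adverse event rate p and an unreported share f; neither is in the documents. With n = 40, the chance of seeing at least one event is 1 − (1 − p(1 − f))^40:

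| Assumed p | f = 0 | f = 25% | f = 50% |
|---|---|---|---|
| 2% | 55% | 45% | 33% |
| 5% | 87% | 78% | 64% |
| 10% | 98.5% | 96% | 87% |

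The table shows which way under-reporting would act. It does not show that the deposit rule causes any.

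**The case against.** The strongest reply is that the rule concerns completion and not harm, and that the protocol has safeguards. Much of this stands.

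- **Reporting.** A reader might infer that the rule penalises a woman for reporting an event. The text does not say so. The loss attaches to non-completion, and sponsor withdrawal for a recurring event is itself optional.
- **Section 8.** A reader might call the two sections contradictory. They are not, for the reason given at step 4.
- **False session logs.** A reader might fear that women will record sessions they did not do. Women are told that the device records use (4.5), adherence is judged from the log and the device memory (5.5), and controller data are downloaded (10.2). This fear is largely answered.
- **Detection of events.** Self-report by phone or email is not the only route. Sections 7.3 and 7.4 add routine contact and review of the log and study materials, 4.5 adds bi-weekly diary checks, and Section 8 seeks post-study activities from women who stop. These routes still depend partly on what the woman discloses.
- **Pressure to continue.** Adherence allows ten missed sessions, so the incentive may be weaker than it looks. Its strength is unknown while completion in 4.5 is undefined.
- **Size of the loss.** The text allows a reduced refund and does not state forfeiture; losing the whole sum is possible only because no minimum is given. Section 10.2 returns the inspected controller to the woman, which would offset the loss, but it describes this for the end of the study, so an early stopper is not clearly covered.
- **Consent form.** Refund terms may be there. It is a separate document and was not available for this review.

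None of these supplies the missing exception in 4.5 or reconciles it with 7.2.

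**Conclusion.** The point holds as a gap in the refund rule and an inconsistency with Section 7.2. As written, a woman who stops, or is withdrawn, because of an adverse event can receive less than her $100, at the discretion of one sponsor official and with no stated criteria. This gives her a financial reason to keep treating and may, indirectly, discourage reporting.

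A reader might go further and put a number on the bias, for example that each withheld event lowers a group's rate by 1/20 = 5 percentage points. The documents do not support that. Section 2.2 defines safety by review of adverse events and the absence of a serious one, with no group event rate or denominator, and nothing in the documents allows under-reporting to be estimated. That the safety result is weakened is a plausible risk, not a demonstrated effect.

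The conclusion rests on the protocol text alone and assumes that the consent form does not already contain the exception. The point should be corrected; it does not call the design into question.

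**What to change.** In Section 4.5, state that the full deposit is refunded, without discretion, on return of the controller when a woman stops or is withdrawn because of an adverse event or by sponsor decision. In Section 7.2, replace the statement that no financial risk is foreseen with the deposit and refund terms, and make the consent form match.

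The cost is wording in the protocol and, where needed, the consent form, plus refunds of at most about $1,000 to $1,500, the upper bound worked out above. The sponsor gives up a little leverage on retention but keeps the incentive to return the controller. No change to design, sample size or analysis is needed.

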## 5. STUDY DESIGN & PROCEDURES

## 5.1 Study Type

Case series with two treatment groups.

## 5.2 Number of Subjects

20 subjects per treatment group (40 total). Appreciating that some subjects who are initially enrolled will fail to complete treatment and return the study materials, it is likely that 50-55 subjects will be enrolled. See 9.1 for discussion of the sample size calculation.

## 5.3 Description of Evaluations

This research utilizes validated methods for evaluating the clinical impact of the device/treatment, including several identified in the FDA guidance document regarding clinical studies that investigate urinary incontinence. Urinary incontinence episodes per day data, obtained from the subject's Daily Log, serves as the primary efficacy outcome measure (see 2.2). Analysis of adverse events serves as the primary safety outcome measure (see 2.2). Evaluations utilized throughout the study are described below. See 9.5 for detail regarding strategies for analyzing the data obtained in these evaluations.

- I-QoL Questionnaire (Pre- and Post-study) the Incontinence Quality of Life (I-QoL) questionnaire is validated tool for assessing changes in the degree to which urinary incontinence affects a woman's quality of life (TR-1155-FORM-2). It comprises 22 questions, to which the subject provides a numeric response on a 1-5 scale. The score is the sum of the numeric responses, which can range from 22 to 110. A change of 2.5 points is considered clinically significant. The I-QoL questionnaire is provided to the subjects as part of pre- and post-study materials. Completed questionnaires are returned to Elidah via mail or electronically (see 10.4).
- Pre-Study Incontinence History and Usability Questionnaire (Pre-study) Included in
  the pre-study activity is a questionnaire that investigates each subject's medical history as
  it pertains to incontinence as well as their perceptions and preferences regarding
  incontinence treatments (TR-1155-FORM-1). Some of this information may be utilized in
  post hoc subgroup analysis (see 9.5). It may also be useful in informing strategies for
  Elidah to effectively reach potential patients.
- Daily Log (Baseline week and treatment weeks) Subjects are required to maintain a

## 5.4 Protocol Schedule

The study comprises five stages: Pre-study, Baseline, Verification, Treatment, and Post-Study.

- Pre-Study –The subjects initiate pre-study activity, which includes completion of the I-QoL Questionnaire and the Pre-study Incontinence History. The subject submits the pre-study materials to Elidah (electronically or hardcopy).
- **Baseline** –Concurrently, the subjects maintain the Daily Log for 7 days to establish a baseline of the episodes/day and pads/day measures. No treatment is administered during this period. After 7 days the subjects submit the data to Elidah (electronically or hardcopy). Subjects are instructed that they should not perform baseline activity during menses or if they are ill. Note that it is acceptable to complete or return the Pre-Study materials throughout this 7 day baseline period.
- **Verification** If the 7 day Baseline shows that the subject does not qualify based on urinary incontinence episode exclusion criteria (<1/day, >5/day) then the subject will be disqualified and the device will not be sent. The subject will be notified of disqualification, or if qualified, will be sent a link for deposit payment/hold. Qualifying subjects will be randomly assigned to a treatment group and a corresponding ELITONE-UUI device will be mailed to them.
- Treatment Subjects will self-administer treatment with the ELITONE-UUI device. Subjects will treat 5x/week for six weeks. Each treatment is 20 minutes. No more than one treatment per day. See Section 6 and Table 5-1 for a detailed description of the device and treatment regimen. If subjects are ill or in menses during the 6th study week they are instructed to extend treatment for at least 5 days after menses and/or they are in good health. During the treatment weeks subjects are required to maintain their Daily Log. There is no difference in treatment requirements between the two treatment groups.
- Post-Study Upon completion of treatment subjects complete the post-study requirements, which include the I-QoL questionnaire and a post-study usability questionnaire. Subjects are requested to complete the requirements and return the study materials to Elidah within 3 days of completing treatment. There is no difference in post-study requirements between the two treatment groups.

Table 5-1: Schedule of Subject Activities/Requirements.

Data used in primary and secondary endpoint analysis     Used to establish compliance.	I-QoL Questionnaire	Pre-Study Questionnaire	Number of Self- administered Treatment	Daily Log	Post-Study Usability Questionnaire	Adverse Events
Pre-Study Data	•	•				
Baseline (Week 0)			0	•		
Treatment (Week 1)			5	0		•
Treatment (Week 2)			5	0		•
Treatment (Week 3)			5	0		•
Treatment (Week 4)			5	0		•
Treatment (Week 5)			5	0		•
Treatment (Week 6)			5	•		•
Treatment (Week 7)*			5	•		•
Post-Study Data	•				•	•
* As needed. See description of treatment above.						

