## 1.5 Sample Size and Population

The population includes women ages 21-80 with mild-moderate urge urinary incontinence or mild-moderate mixed urinary incontinence with predominant urge symptoms. The study intends to have 20 women complete the study in each group.

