#### 4. SELECTION AND ENROLLMENT OF PARTICIPANTS

#### 4.1 Inclusion Criteria

All subjects must meet the inclusion criteria below to participate in this study. Any waiver of these inclusion criteria (or the subsequent exclusion criteria) must be approved by the Clinical Director on a case-by-case basis prior to enrolling the subject, and documented in the subject's Case Report Form (TR-1155-FORM-10).

- Predominant urge urinary incontinence as determined by responses to a series of three standard questions from the King's Health Questionnaire; specifically:
  - An affirmative response to "Is it very difficult to control when you have a strong urge to urinate?",

- An affirmative or negative response to "Do you lose urine with physical activities such as coughing, sneezing, running?",
- And, if an affirmative response to the second question, an affirmative response to "Are more of your incontinence episodes due to a strong urge to urinate than to abdominal pressure such as sneezing?"
- Mild-moderate incontinence symptoms as determined by self-reported typical number of accidents of 1 or more per 24 hours. Symptom severity is later verified with data from the Daily Log (See 5.4)

Age: 21-80yGender: Female

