#### 6.5 Stimulation Waveform

The ELITONE device outputs a two part stimulation signal, delivered at 50 Hz and 10 Hz, both modulated at 2000 Hz. The first (50 Hz) part runs for 4 seconds and the second part (10 Hz) runs for 2 seconds. It is generally understood that a 50 Hz stimulation treats SUI and a 10 Hz frequency treats UUI. After these 6 seconds of stimulation the output goes to zero for 6 additional seconds. This on/off cycling of the stimulation continues for the duration of the treatment. Intensity is set by the user, who is instructed to operate the device at a level that is maximally tolerated, but not painful, for the duration of treatment.

The ELITONE-UUI device increases the proportion of the signal that operates at 10 Hz, intending to have a more substantial effect on UUI symptoms. Configurations are as follows:

- Configuration 1 4 seconds at 50 Hz, followed by 4 seconds at 10 Hz, followed by 6 seconds of rest, repeated.
- **Configuration 2** 6 seconds at 10 Hz followed by 6 seconds of rest, repeated. No 50 Hz stimulation is provided in this variant.

These configurations are achievable solely through software changes.

Should one or both configurations be determined to have minimal effect on the UUI, up to two additional configurations may be considered for clinical evaluation. These additional configurations include:

- Additional Configuration 3 4 seconds at 50 Hz, followed by 4 seconds at 10 Hz, followed by 6 seconds of rest, repeated for 10 minutes. Then, 6 seconds at 10 Hz followed by 6 seconds of rest, repeated for 10 minutes.
- Additional Configuration 4 Current ELITONE stimulation as defined above.

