## 9.2 Randomization

Subjects are assigned to a treatment group at the time the device is shipped to the subject. Assignments are made alternating between Group 1 and 2 until enrollment is complete.

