- Change in urgency episodes without a leak Differences in mobility, activity, etc. may impact whether a subject can get to a toilet before an urgency leak occurs. Analysis of episodes without leaks will occur in the same manner as the "with leak" data.
- Change in pad use Reduction in pad usage will be assessed as a percent change relative to the baseline, and as a response rate, wherein a 50% reduction is considered clinically significant. Subjects who do not use a pad during the baseline week will be excluded from the analysis.
- Change in daily bathroom visits / Change in nighttime bathroom visits Descriptive statistics as defined above.
- I-QoL Incontinence Quality of Life scores will be analyzed with respect to a change from baseline. Responders will be those with an I-QoL score increase of 2.5 points, which is defined in the FDA guidance as clinically significant.

Usability surveys will solicit subject feedback pertaining to their experience with the product. Appropriate statistical methods will be used in reporting these subjective measures.

In addition to characterizing outcome measures as a change in value/score (i.e. percent reduction) or a clinically meaningful response (e.g. ≥50% change), post hoc analyses may investigate outcome measures using analysis of covariance (ANCOVA), wherein baseline values are modeled as covariates, which has the advantage of accounting for variation in the magnitude

of the baseline. Additional post hoc ANCOVA may be performed with covariates including age, type of incontinence, BMI or other potentially relevant variables.

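### Assignment uses one sequence that ignores pure urge versus mixed incontinence, although type is known beforehand and bears on the configurations compared; a second sequence would give a small, cheap gain in balance

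*Combined protocol and SAP*

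**What the plan says.** **Assignment.** Section 9.2 states: "Subjects are assigned to a treatment group at the time the device is shipped to the subject". It continues: "Assignments are made alternating between Group 1 and 2 until enrollment is complete". Section 5.4 describes the same step as random: "Qualifying subjects will be randomly assigned to a treatment group and a corresponding ELITONE-UUI device will be mailed to them". Neither section names a stratification factor. The single sequence is stated in 9.2; the sentence in 5.4 shows only that no stratum is mentioned.

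**Type of incontinence.** Section 1.5 admits women with urge incontinence and women with "mild-moderate mixed urinary incontinence with predominant urge symptoms". Section 4.1 accepts either answer to the stress-leak question, so yes or no separates mixed from pure urge. Section 4.3 says of the screening survey: "Responses are maintained electronically in a Screening Log". Eligibility is judged on those answers, so type is on file before any device ships.

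**Configurations.** Section 6.5 says: "It is generally understood that a 50 Hz stimulation treats SUI and a 10 Hz frequency treats UUI". Configuration 1 gives 4 seconds at 50 Hz and 4 seconds at 10 Hz. Configuration 2 gives 10 Hz only.

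**Analysis.** Section 9.5 takes stress and urge leaks together as the primary outcome and reports an unadjusted mean and SD of percent reduction per group. Post hoc ANCOVA is optional, with "covariates including age, type of incontinence, BMI or other potentially relevant variables". Sections 2.3 and 9.5 let group differences inform the choice of configuration. Section 9.5 adds that the study is not designed for a rigorous comparison between groups.

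**The concern.** On the protocol's own account of the two frequencies, type is the baseline factor most likely to interact with configuration. A mixed woman's stress leaks count in the primary outcome, yet Configuration 2 lacks the component said to treat them. If one group happens to hold more mixed women, part of the observed difference reflects who was in the group and not what the device did. Nothing in the assignment rule limits this, and the planned group summary does not correct for it.

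What is at stake is the informal choice between configurations. Two other provisions use the same group results: section 6.5 may bring in further configurations if one or both show minimal effect, and section 9.6 allows pooling if the groups are shown to be homogeneous.

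The point is separate from whether alternation counts as random. A properly random single list leaves type just as free to vary.

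**Working it through.** **The plan's own figures.** The plan gives no figure for balance by type. Its sample sizes in section 9.1 (31, 16 and 12) compare active with sham treatment. An unpooled two-proportion formula at two-sided 5% and 90% power (not stated in the plan) gives 31.1, 15.3 and 11.2, close to the stated sizes. These do not bear on balance between configurations; only the resulting 20 per group does.

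**Inputs**
- n = 20 per group (sections 5.2 and 9.1).
- Mixed share p: not in the documents; assumed 30-70%.
- Gap g between types in percent reduction: not in the documents; assumed 20-30 points, with 10 as a lower case.

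**1. Spread of the imbalance.** If type is unrelated to shipment order, the counts of mixed women are two independent Binomial(20, p) variables, under alternation or a random list. The SD of the difference in share is √(2p(1−p)/20):
- p = 0.3 or 0.7: √(0.42/20) = 0.145
- p = 0.5: √(0.50/20) = 0.158

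**2. Probability of a notable imbalance (exact)**

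| Mixed share | 4 or more of 20 (≥20 points) | 6 or more of 20 (≥30 points) |
|---|---|---|
| 30% or 70% | 0.226 | 0.056 |
| 50% | 0.268 | 0.081 |

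Counting 25 assigned per group instead (50 of the expected 50-55), 20 points or more occurs in 16-20% of trials.

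**3. Shift in the contrast for a 20-point imbalance**
- Gap under both configurations: 0.20 × g = 4 points (g = 20) to 6 points (g = 30).
- Gap under one configuration only, imbalance symmetric: that group is 10 points from the average share, so 0.10 × g = 2 to 3 points.
- With g = 10: 2 points and 1 point respectively.

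The second line matches the mechanism in section 6.5 more closely, since the argument is that mixed women fare worse where 50 Hz is absent.

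**4. Comparison with sampling error.** The plan gives no SD for percent reduction, so this uses responder rates, with the same gaps read on that scale. The SE of the group difference is √(2r(1−r)/20): 0.158 at r = 0.50 and 0.137 at r = 0.75, or about 14-16 points. With the gap under both configurations, the SD of the shift over all possible assignments is g × (0.145 to 0.158), which is 2.9-4.7 points for g = 20-30.

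**5. Most that balancing could gain.** With p = 0.5, g = 0.30 and r = 0.5, type explains 0.25 × 0.30² / 0.25 = 0.09 of the variance. Removing it reduces the SE by 1 − √0.91 = 0.046, about 5%. At r = 0.75 the figures are 0.0225/0.1875 = 0.12 and 1 − √0.88 = 0.062, about 6%.

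**6. After the change.** Alternating within each type holds the groups to a difference of one mixed woman at assignment (1/20 = 5 points). Permuted blocks of 4 within type hold it to two (10 points).

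**The case against.** The strongest reply is that this is a descriptive case series. Its primary endpoint is each woman's change from her own baseline, and its benchmark in section 9.1 is a 50% reduction or responder rate. Imbalance between groups does not confound those within-subject changes, and section 9.5 disclaims rigorous comparison. This stands, and it limits the point to the informal choice of configuration.

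Second, a reader might infer that the single sequence biases the comparison. The documents do not support that. If type is unrelated to shipment order, the imbalance averages zero and is already part of the sampling error.

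Third, a 20-30 point gap may be high. Mixed women qualify only if urge episodes outnumber stress episodes. Suppose, for illustration, that urge leaks fall by 60% and 10 Hz does nothing for stress leaks. The gap is then 60 × the stress share of leaks, so 20-30 points needs a share of 20/60 = 33% to 30/60 = 50%, the upper end being the eligibility limit. This also stands; smaller gaps give proportionally smaller shifts.

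Fourth, the plan partly covers the issue. Urge leaks are analysed separately as a secondary outcome, and type is named as a possible covariate. Both help but do not settle it. Section 9.5 itself says some women cannot readily tell the two kinds of leak apart, and the covariate analysis is optional and post hoc.

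Finally, balance does not resolve an interaction, and the stratifier is one self-reported answer. Both are true. The first is a reason to show results by type as well.

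**Conclusion.** The point holds as a low-priority, inexpensive improvement. The plan lets type vary freely between groups although type is known before assignment and, by the protocol's own rationale, relevant to the contrast. An imbalance of 20 points or more is expected in 23-27% of trials and would move the contrast by about 2-3 points if the type gap exists under one configuration only, or 4-6 points if under both. Those figures rest on an assumed mixed share of 30-70% and an assumed gap of 20-30 points; the documents give neither.

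It would go too far to read this as a systematic distortion of the configuration comparison, or as a threat to the efficacy result. The shift is chance variation, well below a sampling error of about 14-16 points for responder rates, and the change from baseline is not confounded by it.

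**What to change.** - **Sections 9.2 and 5.4:** keep two assignment sequences, one for women answering no to the stress-leak question and one for women answering yes, and draw each woman's group from her own sequence at shipment. This does not by itself make the sequences random or concealed, which is a separate matter.
- **Section 9.5:** pre-specify the between-group difference adjusted for type, or combined across type, in place of the optional post hoc type covariate. Show within-type results as descriptive only.

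**Cost.** One more list and a sentence or so in each section; no new data and no extra subjects. With alternation in each sequence, group totals may differ by one or two.

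**Limits.** At a 30-70% mixed share, within-type cells hold about 6-14 women per group (20 × 0.3 to 20 × 0.7). At responder rates near 50%, the SE of a within-type difference is √(0.5/14) = 19 to √(0.5/6) = 29 points, so these results should not drive the choice. Dropout from 50-55 enrolled to 40 completers, or restriction to adherent subjects, can bring back some imbalance. The assignment change must be made before devices ship; after that, only the analysis change remains available.
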